5.5.1.3. Corticosteroid Endpoints

Corticosteroid-free related endpoints will be evaluated for all participants in the FAS, and for those receiving corticosteroids at baseline. Clinical remission is defined as given in Section 5.3.1. Other corticosteroid related endpoints will be evaluated at all applicable timepoints.

- Corticosteroid-free clinical remission at Week 24: Defined as being in clinical remission at Week 24 and not receiving corticosteroids at Week 24
- Corticosteroid-free clinical remission at Week 24 among participants who were receiving concomitant corticosteroids at baseline
- Corticosteroid-free clinical remission at Week 48: Defined as being in clinical remission at Week 48 and not receiving corticosteroids at Week 48
- Corticosteroid-free clinical remission at Week 48 among participants who were receiving concomitant corticosteroids at baseline
- 8-week corticosteroid-free clinical remission at Week 48: Defined as being in clinical remission at Week 48 and not having received corticosteroids between Week 40 and Week 48
- 8-week corticosteroid-free clinical remission at Week 48: Defined as being in clinical remission at Week 48 and not having received corticosteroids between Week 40 and Week 48 among participants who were receiving concomitant corticosteroids at baseline
- 12-week corticosteroid-free clinical remission at Week 48: Defined as being in clinical remission at Week 48 and not having received corticosteroids between Week 36 and Week 48
- 12-week corticosteroid-free clinical remission at Week 48: Defined as being in clinical remission at Week 48 and not having received corticosteroids between Week 36 and Week 48 among participants receiving who were receiving concomitant corticosteroids at baseline
- Elimination of concomitant corticosteroids at Week 48 among participants who were receiving concomitant corticosteroids at baseline
- Elimination of concomitant corticosteroids for at least 8 weeks prior to Week 48 among participants who were receiving concomitant corticosteroids at baseline
- Elimination of concomitant corticosteroids for at least 12 weeks prior to Week 48 among participants who were receiving concomitant corticosteroids at baseline
- Average daily prednisone-equivalent corticosteroid dose (excluding budesonide and beclomethasone dipropionate) at each visit, and change from baseline, through Week 48 among participants who were receiving concomitant corticosteroids for the treatment of UC at baseline

• Time to being corticosteroid-free prior to Week 48 among participants who were receiving concomitant corticosteroids at baseline

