5.5.4. Analysis Methods

Unless otherwise specified, the exploratory endpoints listed and defined in Sections 5.5.1 to 5.5.3 will be analyzed based on the FAS according to the randomized intervention group, regardless of the intervention actually received.

No confirmatory tests will be performed on exploratory endpoints, regardless of the significance for primary and secondary endpoints. Nominal p-values will be presented without adjustments for multiple comparisons.

Descriptive statistics (mean, median, SD, IQ range, minimum, and maximum) will be used to summarize continuous variables. Counts and percentages will be used to summarize categorical variables. Graphical data displays (e.g., line plots) may also be used to summarize the data.

Binary endpoints

The main estimand approach and the estimator used for the secondary endpoints (Section 5.4.1.2) will be used to summarize and compare binary endpoints. Intercurrent events will be handled as specified in Table 6.

The handling of ICEs specified in Section 5.4.1.2 will be applied to each of the above binary endpoints. Participants with ICEs in categories 1-4 and 6 will be considered not to have achieved the binary endpoint, while observed values will be used for participants experiencing an ICE in category 5.

Participants with any missing data for an endpoint after application of ICE handling rules will be imputed as not having achieved the associated binary endpoint. Binary endpoints will be summarized with the number and percentage of participants who achieve the endpoint by intervention group. To compare the proportion of participants achieving the endpoints, MH tests stratified by the ADT-IR status (Yes/No), and Mayo endoscopy subscore at baseline (moderate [2] or severe [3]) will be provided. In case of rare events, Fisher's exact test will be used for intervention comparisons.

Continuous endpoints

For continuous endpoints, handling rules for ICEs as defined in Table 6:

- Composite strategy (categories 1-4 and 6): Baseline values will be assigned from the point of ICE onward
- Treatment policy strategy (category 5): Observed values will be used, if available

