6.14. Appendix 14 Detailed Prohibited Changes in UC Medications Rules

[figure not shown]
Participants had a prohibited change in UC medication described below are considered to have experienced ICE 2 as defined in Table 6:

[figure not shown]
- Initiation of restricted medications (rectal 5-ASA compounds, parenteral or rectal corticosteroids, including budesonide and beclomethasone dipropionate)
- Initiation of the following prohibited concomitant therapies
 - Immunomodulatory agents other than 6-MP, AZA, or MTX (eg, 6-thioguanine, cyclosporine, mycophenolate mofetil, tacrolimus, sirolimus, ozanimod, tofacitinib, and other JAK inhibitors).
 - Immunomodulatory biologic agents (eg, TNFα antagonists, ustekinumab, vedolizumab, abatacept, anakinra).
 - Experimental IBD medications (eg, upadacitinib, etrolizumab, brazikumab, mirikizumab, risankizumab) or other investigational medications/therapies.
 - Thalidomide or related agents
- Initiation of oral corticosteroids (including budesonide and beclomethasone dipropionate) due to worsening of disease.
- Increase in the dose of oral corticosteroids (excluding budesonide and beclomethasone dipropionate) > 5 mg/day (prednisone equivalent) above the baseline dose due to worsening of disease:
 - Any number of days with increase from Week 0 through Week 12
 - 3 days or more with increase from Week 12 through Week 24
 - 7 days or more with increase from Week 24 through Week 48
- Increase in the dose of oral budesonide > 3 mg/day above the baseline dose due to worsening of disease:
 - Any number of days with increase from Week 0 through Week 12
 - 3 days or more with increase from Week 12 through Week 24
 - 7 days or more with increase from Week 24 through Week 48
- Increase in the dose of oral beclomethasone dipropionate > 5 mg/day above the baseline dose due to worsening of disease:
 - Any number of days with increase from Week 0 through Week 12
 - 3 days or more with increase from Week 12 through Week 24
 - 7 days or more with increase from Week 24 through Week 48
- Any switch among oral budesonide, oral beclomethasone dipropionate or other oral corticosteroids (excluding prednisone equivalent changes) due to worsening of disease.
- Initiation of oral 5-ASA compounds due to worsening of disease.
- Increase above baseline in the dosage of oral 5-ASA compounds due to worsening of disease.

- Change from one oral 5-ASA compound to another 5-ASA compound due to worsening of disease.

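### For the corticosteroid-dose endpoint, assigning the baseline value after ICE 2 replaces a disease-driven steroid increase above baseline with a change of zero

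*SAP*

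**What the plan says.** SAP 5.5.1.3 defines the endpoint as "Average daily prednisone-equivalent corticosteroid dose (excluding budesonide and beclomethasone dipropionate) at each visit", together with its change from baseline, through Week 48, among participants receiving corticosteroids for UC at baseline. It gives no rule of its own for intercurrent events.

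SAP 5.5.4 therefore governs: "Unless otherwise specified, the exploratory endpoints listed and defined in Sections 5.5.1 to 5.5.3 will be analyzed" by the methods set out there. For continuous endpoints the rule is "Composite strategy (categories 1-4 and 6): Baseline values will be assigned from the point of ICE onward". Only category 5 (COVID-19 or regional-crisis discontinuation) keeps observed values.

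SAP Appendix 14 states that participants with a listed medication change "are considered to have experienced ICE 2 as defined in Table 6". One listed change is a rise in oral corticosteroid, other than budesonide and beclomethasone, of "> 5 mg/day (prednisone equivalent) above the baseline dose due to worsening of disease". The rise must last any number of days up to Week 12, at least 3 days in Weeks 12 to 24, or at least 7 days in Weeks 24 to 48.

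SAP 5.3.2.1 explains the composite strategy: an event in categories 1 to 4 or 6 counts as an unfavourable outcome.

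**The concern.** For a symptom score, going back to baseline is a penalty, because the participant is treated as having gained nothing. For steroid dose after a steroid increase it works the other way. The participant is by definition more than 5 mg/day above baseline when the event occurs, and the rule brings the analysed dose down to baseline. It does so at every later visit through Week 48, so later recorded doses cannot correct it.

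The outcome variable thus defines the event, and the event then overwrites the outcome with a more favourable value. The sustained, disease-driven increases that a steroid-dose endpoint should show are the ones removed. At stake is how far the by-visit mean dose, its change from baseline and the nominal treatment comparison for this endpoint can be interpreted.

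**Working it through.** The plan gives no expected dose, standard deviation, power or event rate for this endpoint, so there is no figure to reproduce. The check applies the two SAP rules to example doses and then works out the effect on group means.

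**Inputs from the documents**
- ICE 2 trigger: more than 5 mg/day above baseline, due to worsening, with the day thresholds above (SAP Appendix 14).
- Replacement: analysed dose = baseline dose from the event onward (SAP 5.5.4).
- Maximum entry dose: 20 mg/day prednisone equivalent (Protocol 5.1, criterion 9.1).
- Dosage and treatment period of concomitant therapy are recorded to the last study visit (Protocol 6.8). Participants whose UC medication changes keep attending visits (Protocol 6.8.1).

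**Step 1. Individual participants** (doses in mg/day; increase due to worsening unless stated)

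| Baseline | Recorded | Days and period | ICE 2? | Recorded change | Analysed change |
|---|---|---|---|---|---|
| 20 | 40 | 14, Weeks 12–24 | yes | +20 | 0 |
| 20 | 30 | 14, Weeks 24–48 | yes | +10 | 0 |
| 10 | 40 | 28, Weeks 24–48 | yes | +30 | 0 |
| 5 | 15 | 10, Weeks 0–12 | yes | +10 | 0 |
| 20 | 25 | 28, Weeks 12–24 | no, not above 5 | +5 | +5 |
| 20 | 40 | 2, Weeks 12–24 | no, too short | +20 | +20 |
| 20 | 40 | 6, Weeks 24–48 | no, too short | +20 | +20 |
| 20 | 40 | 14, Weeks 12–24, not due to worsening | no | +20 | +20 |

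A brief burst is kept in full, while the same dose held for longer becomes zero.

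**Step 2. Arm means.** Let f be the share of baseline steroid users in an arm who have had such an ICE 2, and x the amount by which their recorded dose exceeds baseline at the visit. With complete data and simple means:
- the arm's mean change is lowered by f × x;
- the between-arm difference shifts by (f_placebo − f_guselkumab) × x.

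Both f and x are assumptions. Shift in the difference, in mg/day:

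| x | 10% vs 5% | 20% vs 10% | 30% vs 10% |
|---|---|---|---|
| 10 | 0.5 | 1.0 | 2.0 |
| 20 | 1.0 | 2.0 | 4.0 |
| 30 | 1.5 | 3.0 | 6.0 |

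**Step 3. One scenario in full** (assumed: everyone starts at 20; participants without the event taper to 0; participants with it are at +20; shares 30% placebo, 10% guselkumab)
- Recorded, placebo: 0.30 × 20 + 0.70 × (−20) = −8. Guselkumab: 0.10 × 20 + 0.90 × (−20) = −16. Difference −8.
- Analysed, placebo: 0.30 × 0 + 0.70 × (−20) = −14. Guselkumab: 0.10 × 0 + 0.90 × (−20) = −18. Difference −4.

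The 4 mg/day lost equals (0.30 − 0.10) × 20.

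**Step 4. Other events can push the opposite way.** On the recommended taper (Protocol 6.8.1.1, Table 4), 20 mg/day falls by 5 per week to 10 (2 weekly steps) and then by 2.5 per week to 0 (4 steps). That is about 6 weeks from Week 12, or near Week 18. A placebo participant who meets rescue criteria at Week 16 (ICE 4) and completes the taper has a recorded change of −20 but an analysed change of 0, so is moved up by 20. If r is the share of such participants in an arm, the difference moves by (r_placebo − r_guselkumab) × 20 in the opposite direction. Against the 20% versus 10%, x = 20 cell above (2.0 mg/day), an excess of 10 percentage points in r on placebo gives 0.10 × 20 = 2.0 and cancels it.

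**The case against.** The strongest reply is that baseline assignment is still a penalty here. Tapering is mandatory from Week 12 unless medically not feasible, so by about Week 18 a participant held at 20 mg/day is scored as much as 20 mg/day worse than a peer who tapered on schedule. This is true relative to peers. It does not rescue the rule relative to the participant's own record: someone at 40 mg/day is scored 20 mg/day better than recorded.

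A reader might infer that the planned analysis as a whole understates the steroid-sparing effect of guselkumab. The documents do not support that. Participants who had tapered before ICE 3, 4 or 6 are moved up to baseline, which can widen the difference, and no event rates are given from which to net the two effects. A reader might also infer that all steroid increases are lost. Increases of 5 mg/day or less, those too short or not due to worsening, and re-escalation no higher than the baseline dose trigger no ICE 2.

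It might also seem natural to use recorded doses after every event. That is debatable. After rescue, placebo would be credited with tapering achieved on guselkumab, whereas even the SAP's supplementary treatment-policy estimands keep ICEs 1, 2 and 4 composite (SAP 5.3.2.2.1 and 5.4.1.3.1). After discontinuation, participants have an early-discontinuation visit and a safety follow-up about 12 weeks after the last dose, so doses to Week 48 would often be missing.

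Finally, the endpoint carries nominal p-values only and is not named in the exploratory list of Protocol Section 3. This limits the consequence but does not remove the error.

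**Conclusion.** The point holds in a limited form. For this endpoint, the SAP 5.5.4 rule is wrong for ICE 2 when the event is itself a qualifying steroid increase: while the recorded dose stays above baseline, the analysed change of zero is better than the recorded one and contradicts the SAP's own view of the event as unfavourable. This follows from the text and needs no assumed rates.

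The group-level size does need assumptions. Over the assumed grid, this component shifts the between-arm difference by 0.5 to 6 mg/day, against an entry maximum of 20 mg/day. It would be smaller for increases just above the 5 mg/day threshold (about 0.05 × 5 = 0.25 mg/day at 10% versus 5%), and zero if the shares were equal. These are simple-mean figures; model-based estimates from the MMRM need not match them exactly. The net bias over all intercurrent events is unknown in size and direction.

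The primary and secondary tests are untouched. The binary steroid-free endpoints are also safe, since an ICE in categories 1 to 4 or 6 counts as failure there.

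**What to change.** Add one sentence to SAP 5.5.4 or 5.5.1.3: for average daily prednisone-equivalent dose and its change from baseline, after ICE 2 the analysed value at each visit is the higher of the recorded and the baseline dose, and the baseline dose where none is recorded. No participant then scores better than baseline after ICE 2, so the composite intent is kept, and recorded increases are no longer hidden. In the Step 3 scenario the difference returns to −8 mg/day.

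Keep the composite rule for the other events in categories 1, 3, 4 and 6. Optionally, add a supplementary summary using recorded doses after all events, labelled as including doses taken on rescue guselkumab and as incomplete after discontinuation.

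The cost is one sentence and a small programming change. Concomitant doses are already recorded, no new data are needed, and the type I error is unaffected. If the Week 48 analysis has already been run, report the corrected version as a labelled supplementary analysis.

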5.5.2. Endpoints Related to Health-Related Quality of Life

Health-related quality of life endpoints are based on the Inflammatory Bowel Disease Questionnaire (IBDQ), Patient-Reported Outcomes Measurement Information System (PROMIS-29), and UC Patient-reported outcomes signs and symptoms (UC-PRO/SS).

5.5.2.1. Inflammatory Bowel Disease Questionnaire (IBDQ) Related Endpoints

The IBDQ⁴⁾ is a validated, 32-item, self-reported questionnaire for participants with IBD that will be used to evaluate the disease specific HRQoL, across 4 dimension scores: Bowel symptoms (loose stools, abdominal pain), systemic functions (fatigue, altered sleep pattern), social function (work attendance, need to cancel social events), and emotional function (anger, depression, irritability). Scores range from 32 to 224, with higher scores indicating better outcomes.

The individual IBDQ dimensions will be calculated when no more than 1 item is missing in the dimension. If an item is missing, it will be estimated using the average value across the non-missing items. If any of the 4 dimensions of the IBDQ cannot be calculated, then the total IBDQ score cannot be calculated and will be missing for that visit.

The following will be evaluated at all applicable timepoints:

- The change from baseline over time in the total score of the IBDQ
- The change from baseline over time in each of the 4 dimensions of the IBDQ
- A \geq 16-point improvement from baseline in the IBDQ score
- A > 20- point improvement from baseline in the IBDQ score
- IBDQ remission, defined as total IBDQ score ≥170 (Irvine et al, 1994⁴); Higgins et al, 2005³)
- Sustained improvement: A ≥ 16-point improvement from baseline in the IBDQ score at both Week 12 and Week 48
- Sustained IBDQ remission: Total IBDQ score ≥170 at both Week 12 and Week 48

5.5.2.2. PROMIS-29 Related Endpoints

The PROMIS-29 is a validated general health profile instrument that is not disease specific. It is a collection of short forms containing 4 items for each of 7 domains (depression, anxiety, physical function, pain interference, fatigue, sleep disturbance, and ability to participate in social roles and activities). PROMIS-29 also includes an overall average pain intensity 0-10 numeric rating scale (NRS). Norm-based scores have been calculated for each domain on the PROMIS measures, with a score of 50 representing the mean or average for the reference population. On symptom-oriented domains of PROMIS-29 (anxiety, depression, fatigue, pain interference, and sleep disturbance), higher scores represent worse symptomatology. On the function-oriented domains (physical functioning and social role), higher scores represent better functioning.

The following will be evaluated at all applicable timepoints:

- The change from baseline over time in each of the 7 domains T-scores of PROMIS-29 and the pain intensity
- A \geq 5-point improvement in each of the 7 domains T-scores of PROMIS-29 over time
- A \geq 7-point improvement in each of the 7 domains T-scores of PROMIS-29 over time
- A \geq 9-point improvement in each of the 7 domains T-scores of PROMIs-29 over time
- $A \ge 3$ -point improvement in the PROMIS-29 pain intensity over time
- A \geq 3-point improvement from baseline in the PROMIS-29 pain intensity over time among the participants with pain intensity \geq 3 at baseline

5.5.2.3. UC-PRO/SS Related Endpoints

The UC-PRO/SS measure was developed to standardize the quantification of gastrointestinal signs and symptoms of UC through direct report from patient ratings. It is a 9-item daily diary designed to quantify the effects of treatment on patient-reported signs and symptoms of UC (see Appendix 15). The UC-PRO/SS includes two scales – bowel signs and symptoms (6 items) and functional symptoms (3 items). Each scale is scored separately; there is no total score for the UC-PRO/SS. Only eligible days as defined for the Mayo score (see Section 5.3.1) will be used for analyses of the UC-PRO/SS.

The following will be evaluated at all applicable timepoints:

- The change from baseline in the weekly average score for each of the 9 items assessed by the UC-PRO/SS
- The change from baseline in the bowel signs and symptoms scale of UC assessed by UC-PRO/SS
- No bowel urgency, defined as a rounded weekly average score of 0 in question 7 of the UC-PRO/SS, over time
- Resolution of bowel urgency, defined as a rounded weekly average score of 0 in question 7 of the UC-PRO/SS among those with a rounded weekly average bowel urgency score ≥1 at baseline
- No bowel urgency (alternative definition), defined as a score of '0' in question 7 of the UC-PRO/SS on the three days closest to each visit, over time
- Resolution of bowel urgency (alternative definition), defined as a score of '0' in question 7 of the UC-PRO/SS on the three days closest to each visit among those with a bowel urgency score ≥1 for at least one of the three days closest to baseline
- No abdominal pain, defined as a rounded weekly average score of 0 in question 8 of the UC-PRO/SS, over time
- Resolution of abdominal pain, defined as a rounded weekly average score of 0 in question 8 of the UC-PRO/SS among those with a rounded weekly average abdominal pain score ≥1 at baseline

- No abdominal pain (alternative definition), defined as a score of '0' in question 8 of the UC-PRO/SS on the three days closest to each visit, over time
- Resolution of abdominal pain (alternative definition), defined as a score of '0' in question 8 of the UC-PRO/SS on the three days closest to each visit among those with an abdominal pain score ≥1 for at least one of the three days closest to baseline
- No incontinence, defined as a rounded weekly average score of '0' in question 5 of the UC-PRO/SS, over time
- Resolution of incontinence, defined as a rounded weekly average score of '0' in question 5 of the UC-PRO/SS among those with a rounded weekly average incontinence score ≥1 at baseline
- no incontinence (alternative definition), defined as a score of '0' in question 5 of the UC-PRO/SS on the three days closest to each visit, over time
- Resolution of incontinence (alternative definition), defined as a score of '0' in question 5 of the UC-PRO/SS on the three days closest to each visit among those with an incontinence score ≥1 for at least one of the three days closest to baseline
- The change from baseline in the functional symptoms scale of UC assessed by UC-PRO/SS
- A clinically meaningful change (defined as an improvement from baseline of ≥ 5 points) in the bowel signs and symptoms scale assessed by UC-PRO/SS
- A clinically meaningful change (defined as an improvement from baseline of ≥ 1.5 points) in the functional symptoms scale assessed by UC-PRO/SS
- A clinically meaningful change in the urgency assessed by UC-PRO/SS, defined as follows:
 - Improvement from baseline ≥ 1 point for participants with a baseline weekly average score for item #7 of at least 1 point
 - Improvement from baseline ≥ 2 points for participants with a baseline weekly average score for item #7 of at least 2 points

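### The UC-PRO/SS bowel and functional meaningful-change endpoints have no baseline minimum; add a baseline-restricted version beside the planned FAS analysis

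*SAP*

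**What the plan says.** SAP 5.5.2.3 lists three kinds of clinically meaningful change for the UC-PRO/SS. Two concern the scale scores and carry no condition on baseline:

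- bowel scale: "A clinically meaningful change (defined as an improvement from baseline of ≥ 5 points) in the bowel signs and symptoms scale assessed by UC-PRO/SS"
- functional scale: "A clinically meaningful change (defined as an improvement from baseline of ≥ 1.5 points) in the functional symptoms scale assessed by UC-PRO/SS"

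The third concerns urgency (item 7) and does carry one. Its first version reads "Improvement from baseline ≥ 1 point for participants with a baseline weekly average score for item #7 of at least 1 point". A second version, with a 2-point threshold, is likewise confined to those who start at 2 or more.

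SAP 5.5.2.2 gives PROMIS-29 pain intensity both forms. A 3-point improvement is listed first without a condition, and then as an "improvement from baseline in the PROMIS-29 pain intensity over time among the participants with pain intensity" of at least 3 at baseline.

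Unless stated otherwise, SAP 5.5.4 says that exploratory endpoints "will be analyzed based on the FAS according to the randomized intervention group, regardless of the intervention actually received". Binary ones use the estimator of the secondary endpoints, which SAP 5.4.2.1 gives as the common risk difference with Mantel-Haenszel weights. Missing data count as failure: "Participants with any missing data for an endpoint after application of ICE handling rules will be imputed as not having achieved the associated binary endpoint". P-values are nominal.

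Protocol 9.4.6.1 names the proportion of participants with meaningful change in the two domain scores and leaves the definition to the SAP.

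**The concern.** A required fall of 5 or 1.5 points is out of reach for someone who starts below that value, if the scale cannot go below 0. Such a participant stays in the FAS denominator and is a non-responder whatever the treatment does.

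The entry criteria (SAP 1.2: modified Mayo score 5 to 9, rectal bleeding subscore at least 1, endoscopy subscore at least 2) set no minimum on either UC-PRO/SS scale. A low baseline is easier to imagine on the functional scale than on the bowel scale, because entry requires active bowel disease.

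What is at stake is how the result reads. The reported risk difference would depend partly on how many participants entered with few of the symptoms in question. It would also rest on a different denominator from the urgency endpoint a few lines below it. Some power would be lost as well.

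**Working it through.** **Inputs from the documents.** Thresholds of 5 and 1.5 points (SAP 5.5.2.3); FAS denominator and risk-difference estimator (SAP 5.5.4, 5.4.2.1); 133 participants per group, so 266 v 133 at Week 12 for combined guselkumab against placebo (SAP 1.2 and 3); two-sided 0.05.

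**Inputs that are assumed.** The floor of 0 is inferred from item definitions such as "No abdominal pain, defined as a rounded weekly average score of 0 in question 8 of the UC-PRO/SS, over time"; the scale scoring in Appendix 15 is not in the public text. The share s below threshold is not given and is varied from 0% to 40%, equal in both arms. Response rates among those able to respond are not given either; 45% v 30% is the main illustration and 60% v 30% a check.

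**Checking the formula.** The plan states no power for any UC-PRO/SS endpoint, so there is no figure of its own to reproduce on this point. The formula used below, with pooled variance under the null, is

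power = Φ{ [(p1 − p0) − 1.96·√(p̄(1 − p̄)(1/n1 + 1/n0))] / √(p1(1 − p1)/n1 + p0(1 − p0)/n0) }.

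On SAP Section 3 it gives 96.1% for 22% v 8% (stated: above 95%), 90.1% for 20% v 8% and 89.6% for 22% v 9.5% (both stated as 90%). It agrees with the plan.

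**Dilution.** If a share s in each arm cannot respond, the FAS rates are (1 − s)p1 and (1 − s)p0. Then:

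- risk difference = (1 − s)(p1 − p0)
- risk ratio = p1/p0, unchanged
- if p1 = p0 the FAS rates are also equal, so type I error is not inflated

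**Worked case, s = 30%, Week 12.**

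- FAS: rates 0.7 × 45% = 31.5% and 0.7 × 30% = 21.0%, difference 10.5 points, n = 266 and 133. p̄ = (266 × 0.315 + 133 × 0.210)/399 = 0.280. The null standard error is 0.0477 and the alternative 0.0454. Power = Φ[(0.105 − 1.96 × 0.0477)/0.0454] = Φ(0.25) = 60%.
- Restricted: rates 45% and 30%, difference 15 points, n = 186.2 and 93.1. p̄ = 0.400. The standard errors are 0.0622 and 0.0599. Power = Φ[(0.150 − 1.96 × 0.0622)/0.0599] = Φ(0.47) = 68%.

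**Range, 45% v 30%, 266 v 133 before restriction.**

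| s | FAS difference (points) | FAS power | Restricted difference (points) | Restricted power |
|---|---|---|---|---|
| 0% | 15.0 | 83% | 15.0 | 83% |
| 10% | 13.5 | 76% | 15.0 | 79% |
| 20% | 12.0 | 69% | 15.0 | 74% |
| 30% | 10.5 | 60% | 15.0 | 68% |
| 40% | 9.0 | 51% | 15.0 | 61% |

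Restriction recovers only part of the lost power, because fewer participants can contribute. At s = 30%, FAS power is 83.1 − 60.0 = 23.1 points lower than at s = 0, and restriction recovers 68.1 − 60.0 = 8.1 of these.

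**Larger effect.** With 60% v 30% and s = 20%, the difference is 24 points on the FAS and 30 restricted, and power is above 99% either way. Only the reported size of the effect changes.

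The power figures are for an unstratified test; the plan's test is stratified.

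**The case against.** The strongest reply is that the FAS proportion is a legitimate target, and the one the protocol names. It answers what share of all treated participants improve meaningfully, and a participant with little to improve is correctly counted as not having done so. That stands. A reader might infer that the planned analysis understates the effect and should give way to the restricted one. The documents do not support this: nothing in them makes the symptomatic subset the target, and the two pain-intensity versions are listed side by side, unranked, with the unrestricted one first.

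A reader might also infer that all the UC-PRO/SS meaningful-change endpoints are affected, or that dilution is established. Neither holds. Urgency already carries baseline minima, and no baseline UC-PRO/SS distribution is given, so the share below threshold may be nil.

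Further points that stand:

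- Thresholds without a baseline condition are common in this SAP (IBDQ improvement of 16 or 20 points, PROMIS-29 T-score improvements), so the two scales are not an isolated lapse.
- Both scales are also analysed as continuous change from baseline, with adjustment for the baseline score, and that analysis has no fixed failures.
- The endpoints are exploratory with nominal p-values, and the documents set no power target for them.
- Restriction is not a complete cure. With a floor of 0, a functional baseline of exactly 1.5 still requires complete resolution. Restriction also removes participants with no baseline score, whom the FAS version counts as failures; Protocol 4.2 limits PRO collection to countries with translations.

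None of this argues against adding a second version. The restriction uses baseline data only, so it preserves the randomised comparison within the subset, and the same section already uses it for urgency.

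**Conclusion.** The point holds as a minor improvement. The bowel and functional endpoints have no baseline minimum, and on the FAS their risk difference is (1 − s) times the difference among participants able to respond. This rests on a scale floor of 0, which is inferred, and on a share s that the documents do not give.

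At s = 0 there is no effect. Under the assumed 45% v 30%, s between 10% and 40% takes 1.5 to 6.0 points off a 15-point difference, and FAS power at Week 12 is about 3 to 10 percentage points below that of the restricted analysis. Any shift is toward no effect. No confirmatory conclusion depends on it, and the planned FAS analysis remains valid for the question it asks.

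**What to change.** In SAP 5.5.2.3, keep the two FAS endpoints as planned. Beside each, add the same endpoint among FAS participants whose baseline scale score is at least 5 (bowel) or at least 1.5 (functional). This follows the side-by-side form used for PROMIS-29 pain intensity and the baseline condition used for urgency.

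Report by arm, for each scale, the number below threshold and the number with a missing baseline score. These counts supply the unknown share and show how much of any contrast between the two versions comes from missing baselines. If the relevant database lock has passed, label the added rows post hoc.

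The cost is a short change of wording, two extra table rows with the counts, and a smaller denominator in the added rows. No protocol change is needed, because Protocol 9.4.6.1 leaves the definition to the SAP.
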